2.1.2. Secondary Objectives

- To characterize the pharmacokinetic (PK) profile of BGB-DXP593 administered intravenously as a single dose at each dose level in healthy subjects
- To evaluate the potential immunogenicity of BGB-DXP593 administered intravenously as a single dose at each dose level in healthy subjects

2.2. Study Endpoints

2.2.1. Primary Endpoint

- Incidence and severity of treatment-emergent adverse events (TEAEs) and treatment-emergent serious adverse events (SAEs)

2.2.2. Secondary Endpoints

- Changes in vital signs and 12-lead electrocardiogram (ECG) parameters from baseline
- Incidence and magnitude of clinical laboratory abnormalities
- Characterize PK concentration-time profile and PK parameters for BGB-DXP593: C_{max} , AUC_t , AUC_{inf} , AUC_{0-29} , t_{max} , $t_{1/2}$, CL, and V_z as appropriate
- Clinical immunogenicity of BGB-DXP593 evaluated through the detection of ADA over time

3. STUDY DESIGN

3.1. Summary of Study Design

This is a first-in-human, randomized, double-blind, placebo-controlled, single dose escalation study to investigate the safety, tolerability, PK, and immunogenicity of BGB-DXP593 in healthy subjects.

After providing written informed consent, subjects will complete all the screening assessments. After being confirmed as eligible, subjects will be sequentially enrolled for different dose levels.

Two dose levels are planned for eligible subjects to receive a single intravenous dose of study drug (ie, BGB-DXP593 or placebo) at 10 mg/kg or 30 mg/kg, respectively. Another higher dose level will be allowed for dose escalation.

Enrollment will begin at the 10 mg/kg dose level. Escalation to the next dose level will occur 7 days after the last subject at the current dose level has received the study drug, and the safety, laboratory data have been reviewed.

At each dose level, eligible subjects will be randomized at a 3:1 ratio (6 active: 2 control) to the active arm for receiving BGB-DXP593 or to the control arm for receiving the same volume of placebo (ie, normal saline), respectively.

The sentinel dosing will be adopted for each dose level. In the other words, 2 eligible subjects will be randomized at a 1:1 ratio (1 active: 1 control) to receive BGB-DXP593 or placebo on Day 1; and the remaining subjects will be randomized at a 5:1 ratio (5 active: 1 control) to receive BGB-DXP593 or placebo at least 48 hours later, provided satisfactory safety and tolerability is demonstrated for the first 2 subjects randomized and dosed at the dose level.

The planned dose levels and number of subjects are provided in [Table 3](#). Up to 30 subjects (including possible replacement) will be enrolled in the study, which will be conducted in 1 center in Australia.

Subjects are expected to be available for follow-up visits until Day 113 of the study. Subjects will be replaced if they cannot complete the infusion. Subjects may be replaced if they discontinue from the study before Day 29.

Table 3: Planned Dose Levels and Number of Subjects

Dose Level	Number of Subjects ^b	
	Active Arm (BGB-DXP593)	Control Arm (Normal Saline)
A – 10 mg/kg	6	2
B – 30 mg/kg	6	2
C ^a	6	2

Abbreviation: PK, pharmacokinetic.

^a Besides the 2 planned dose levels, one higher dose level will be allowed. The higher dose level will be triggered based on the review of PK data from the first 2 dose levels (see [Section 3.2.2.2](#)).

^b Enrollment up to 30 subjects is permitted if additional subjects are necessary for safety or PK evaluations.

Study Assessments

Subjects will be monitored for safety, tolerability, PK and immunogenicity of BGB-DXP593 throughout the study.

Assessments of safety will include adverse events (AEs), SAEs, clinical laboratory tests, physical examinations, vital signs, and ECGs. A Safety Monitoring Committee (SMC) will periodically monitor safety data.

Adverse events will be graded for severity per the current version of the National Cancer Institute Common Terminology Criteria for Adverse Events (NCI-CTCAE) version 5.0. Refer to Section 9 for additional and specific information regarding AE monitoring and reporting.

PK and ADA sampling will be collected at specific intervals from Day 1 to Day 113 (Appendix 3).

Study procedures and assessments are further detailed in Section 7 and Section 8, respectively, and the Schedule of Assessments can be found in Appendix 1. Specific details regarding dose escalation are described in the following sections.

3.2. Details of Dose Escalation

3.2.1. Starting Dose and Dose Escalation Approach

Dose escalation will occur sequentially in increasing dose levels of study drug. Each dose level of study drug evaluated may be referred to as a cohort or dose level. This is a single dose escalation study, therefore, only 1 dose of BGB-DXP593 or placebo will be administered to each subject.

The starting dose level will be 10 mg/kg. This dose level was chosen based on an overall assessment of toxicology data in cynomolgus monkeys (more details are provided in Section 1.3.2).

Two ascending dose levels for study drug at single doses of 10 mg/kg and 30 mg/kg, are included in the study. Besides the 2 planned dose levels, one higher dose level will be allowed (see details in Section 3.2.2). The projected safety margins at the proposed dose levels reflect favorably on the safety profile of BGB-DXP593 and show that a dose up to 60 mg/kg is expected to provide adequate (> 2 fold) safety margins (Table 2).

3.2.2. Rules for Dose Escalation

The study design allows a gradual dose escalation with intensive safety monitoring to ensure the safety of the subjects. In this single dose escalation study with healthy subjects, the maximum factor for the first dose escalation step will be 4, the maximum factor for the following potential dose escalation step will be 3.

3.2.2.1. Escalation From Dose Level A to Dose Level B

Dose escalation will occur in sequential order after reviewing at least 7 days of safety and laboratory data by the SMC and in the absence of meeting any prespecified pausing criteria (more details are provided in Section 3.3).

An appropriate interval (at least 7 days) between dose levels will require a timely review and evaluation of safety data (eg, AE profile, vital signs, 12-lead ECG, cardiac telemetry, and clinical laboratory safety tests) prior to proceeding to a higher dose level.

The data will be reviewed by the SMC (Section 11.1) who will decide on the next dose level. The data from all the subjects in the previous dose level will be reviewed. Proceeding to the next higher dose level will only occur if the previous dose level was deemed by the SMC to be safe and well tolerated.

Following the review of data from subjects under a dose level, the timing of assessments and/or blood samples may be adjusted for subsequent dose level(s). Additional assessments or sampling times may be added or removed if indicated by the data; however, the maximum blood volume taken from each subject will not exceed 450 mL.

3.2.2.2. Potential Escalation From Dose Level B to Dose Level C

There is an option to explore a third dose level that is higher than 30 mg/kg in this study. The conduct of the third dose level will be triggered based on the review of PK data from the first 2 dose levels.

Pharmacokinetic data from a minimum of 3 subjects per dose level, up to Day 29, will be evaluated to ensure that the PK of BGB-DXP593 is approximately dose proportional and in line with the predicted concentrations and safety margins. The predicted exposure for Dose Level C, based on PK data from the first 2 dose levels, will not exceed the cynomolgus monkey exposure based on C_{max} and combined AUC of the repeat doses at the NOAEL (ie, 300 mg/kg). The data will be reviewed by the SMC (Section 11.1).

3.3. Criteria for Pausing Drug Administration and New Enrollment

The SMC will review the safety and laboratory data at each dose level. If an increased risk for the subjects is suspected during the study, the SMC will recommend to immediately suspend the recruiting of additional participants.

The administration of the study drug and the enrollment of new subjects will pause for the dose level, if any of the following events occurs:

- One or more \geq Grade 4 TEAEs or treatment-emergent SAEs related to study drug as assessed by the investigator in any subject or
- Grade 3 TEAEs related to study drug as assessed by the investigator in 2 or more subjects at the same dose level.

The SMC may recommend keeping the current enrollment plan, opening a repeated cohort at the same dose level, de-escalating to a lower dose level, or terminating the study. For the scenarios of repeated dose level and lower dose level, the number of subjects and randomization ratio will be the same as planned dose levels.

If a repeated cohort evaluation of the same dose level confirms the AE profile previously observed at the dose level, no higher dose level will be tested in this study.

4. SELECTION OF STUDY POPULATION

The specific eligibility criteria for the selection of subjects are provided in Section 4.1 and Section 4.2. The sponsor will not grant any eligibility waivers.

4.1. Inclusion Criteria

Each subject must meet all the following inclusion criteria to be considered eligible for participation in this study:

1. Male and female subjects, 18 to 60 years of age inclusive, at the time of signing the informed consent
2. Subjects are in good general health as determined by the investigator or medically qualified designee, based on a medical evaluation including medical history, physical examination, laboratory tests and cardiac monitoring
3. Body weight \geq 50 kg and body mass index (BMI) within the range 18 to 32 kg/m² (inclusive)
Note: BMI = weight [kg] / (height [m])²
4. Negative serum IgG to the SARS-CoV-2
5. Negative for COVID-19 based on the nasopharyngeal or oropharyngeal swab with the method of real-time reverse transcription-polymerase chain reaction (rRT-PCR)
6. Female subjects of childbearing potential must be willing to use a highly effective method of birth control (see Appendix 5) from the time of study enrollment until 4 months after the single dose of study drug.
7. Male subjects with female partners of childbearing potential must be willing to use a highly effective method of birth control (see Appendix 5) from the time of study enrollment until 4 months after the single dose of study drug.
8. Able to provide written informed consent and can understand and agree to comply with the requirements of the study and the schedule of assessments

4.2. Exclusion Criteria

Subjects who meet any of the following criteria will be excluded from this study:

Medical Histories or Conditions

1. History or presence of cardiovascular, respiratory, hepatic, renal, gastrointestinal, endocrinological, hematological, or neurological disorders capable of significantly altering the absorption, metabolism, or elimination of drugs, constituting a risk to the subject when taking the study drug; or interfering with the interpretation of data
2. Systolic blood pressure $>$ 150 mmHg at screening
3. Any malignancy within the past 5 years except for basal cell or squamous epithelial carcinomas of the skin that have been resected with no evidence of metastatic disease for 3 years

4. Any history of a severe allergic reaction prior to enrollment that has a reasonable risk of recurrence during the study
5. Have a medical history of SARS infection
6. Any acute fever disease or infections
7. Any chronic or clinically significant medical condition that, in the opinion of the investigator, would jeopardize the safety or rights of the subject, including but not limited to: diabetes mellitus type I, chronic hepatitis; or clinically significant forms of: drug or alcohol abuse, asthma (except for childhood asthma), autoimmune disease, psychiatric disorders, or heart disease
8. Platelet disorder or other bleeding disorder may cause injection contraindication
9. Alanine aminotransferase and/or aspartate aminotransferase $> 1.5 \times$ upper limit of normal (ULN)
10. Bilirubin $> 1.5 \times$ ULN (isolated bilirubin $> 1.5 \times$ ULN is acceptable if bilirubin is fractionated and direct bilirubin $< 35\%$)
11. Current or chronic history of liver disease or known hepatic or biliary abnormalities (with the exception of Gilbert's syndrome or asymptomatic gallstones)
12. Average Fridericia's formula (QTcF) > 450 msec (based on triplicate ECGs)
 - NOTE A: The QTc is the QT interval corrected for heart rate according to QTcF, and/or another method. It is either machine-read or manually over-read.
 - NOTE B: The specific formula used to determine eligibility or discontinuation for an individual participant should be determined prior to initiation of the study. In other words, several different formulas cannot be used to calculate the QTc for an individual participant and then the lowest QTc value used to include or discontinue the participant.

Prior/Concomitant Therapy

13. Previous receipt of a licensed or investigational biologic agent (such as, monoclonal antibodies) within 3 months or 5 half-lives (whichever is longer) prior to the randomization
14. Previous receipt of a licensed or investigational nonbiologic agent (such as, those derived from chemical synthesis) within 1 month or 5 half-lives (whichever is longer) prior to the randomization
15. Past or intended use of over-the-counter or prescription medication, including herbal medications, within 28 days prior to the randomization. Use of paracetamol, ibuprofen, and/or vitamins at the recommended dose will be allowed at the investigator's discretion within 28 days prior to the randomization.

Prior/Concurrent Clinical Study Experience

16. Participation in ≥ 4 clinical studies within 12 months prior to the randomization

Diagnostic Assessments

17. Positive human immunodeficiency virus (HIV) antibody test
18. Presence of hepatitis B surface antigen (HBsAg) and/or hepatitis B core antibody (HBcAb) at screening or within 3 months prior to the randomization
19. Positive hepatitis C antibody test result at screening or within 3 months prior to the randomization

NOTE: Participants with positive hepatitis C antibody due to prior resolved disease can be enrolled if a confirmatory negative hepatitis C RNA test is obtained.

20. Positive hepatitis C RNA test result at screening or within 3 months prior to the randomization

NOTE: Test is optional and participants with negative hepatitis C antibody test are not required to also undergo hepatitis C RNA testing.

21. Positive pre-study alcohol/drugs screen

Other Exclusions

22. Immediate family history of seizures, epilepsy, brain or mental disease at the investigator's discretion
23. The total volume of blood loss > 500 mL within 3 months prior to the randomization
24. Sensitivity to any of the study drug or components thereof, or other allergy that, in the opinion of the investigator or medical monitor, contraindicates participation in the study
25. Heavy smokers who have ≥ 15 cigarettes per day

5. STUDY TREATMENT

5.1. Formulation, Packaging, and Handling

5.1.1. BGB-DXP593

BGB-DXP593 is a neutralizing mAb formulated for intravenous injection in a single-use vial (United States Pharmacopeia [USP] type I), containing a total of 300 mg of antibody in 10 mL of buffered isotonic solution. BGB-DXP593 has been aseptically filled in single-use vials with a rubber stopper capped by an aluminum flip-off seal. Five single-use vials are packaged into each carton box. The contents of the label from vials and carton boxes will be in accordance with all applicable local regulatory requirements.

The study drug will be dispatched to the study center only after receipt of the required documents in accordance with applicable regulatory requirements and the sponsor's procedures. The unblinded pharmacist(s) or designated personnel are responsible for maintaining the drug supply inventory and acknowledging receipt of all study drug shipments. The study drug must be stored in a secure area, with access limited to the authorized study center personnel and kept under physical conditions that are consistent with study drug-specific requirements. BGB-DXP593 must be stored at temperatures between 2 °C and 8°C and protected from light.

Refer to the Pharmacy Manual for details regarding intravenous administration, accountability, and disposal. Please also refer to the [BGB-DXP593 Investigator's Brochure](#) for other details regarding BGB-DXP593.

5.1.2. Placebo

Placebo matching BGB-DXP593 is the normal saline (ie, solution of 0.9% sodium chloride) to the required volume. The normal saline will be sourced and provided by the site.

For further details, refer to the Pharmacy Manual for the matching placebo.

5.2. Dosage, Administration, and Compliance

All eligible subjects will be assigned to one of the dose levels. Each subject will receive a single intravenous dose of BGB-DXP593 or matching placebo for 30-60 minutes. The dose of study drug will be based on the subject's actual body weight on the day of study administration.

As a routine precaution, subjects must be monitored for at least 2 hours after the infusion of study drug in an area with resuscitation equipment and emergency agents. The study drug must not be administered concurrently with any other drug.

For safety reasons, dose administration for the first 2 subjects randomized and dosed at each dose level will be monitored for at least 48 hours prior to the remaining subjects receiving the same dose level.

After the starting dose of study drug, the decision to proceed to each subsequent dose level will be made by the SMC at 7 days after the last subject at the current dose level has received the study drug, and all the safety, laboratory data have been reviewed.

Accurate records of the study drug received, dispensed, returned, and disposed of should be maintained in the site's Drug Inventory Log. Please refer to the Pharmacy Manual for details regarding study drug management, drug preparation, storage, and administration.

5.3. Measures to Minimize Bias: Randomization and Blinding

Randomization

At each dose level, eligible subjects will be randomized at a 3:1 ratio (6 active: 2 control) to receive BGB-DXP593 or placebo, respectively. The sentinel dosing will be adopted for each dose level and the randomization ratios for sentinel dosing are provided in Section 3.1.

Site personnel will access the Interactive Response Technology (IRT) system to randomize the treatment assignment. A subject for replacement will receive a unique study subject number and will be assigned to the same treatment as the subject he/she replaces.

Blinding

The study is designed as double-blind for the subjects and the investigator (as well as the site personnel) in order to eliminate observational or performance bias. This is to avoid the systematic differences in assessments on the subject's treatment (ie, BGB-DXP593 or placebo).

The single dose of study drug will be prepared by unblinded pharmacist(s) and administered by blinded study nurse(s). Both the intravenous infusion of BGB-DXP593 and placebo will be colorless. All the follow-up evaluations will be performed by blinded clinic staff.

At the study site, access to the treatment information for each subject is restricted to the unblinded pharmacist(s). Persons directly involved in the clinical conduct of the study will not have access to the treatment allocation prior to database lock.

Regarding the sponsor, the database of this study will be handled as open-label, meaning that the study functions of the sponsor are unblinded (including the medical monitor and study team members from Pharmacovigilance/Drug Safety, Clinical Pharmacology, and Biostatistics with other members as appropriate). The objectives of the study are expected not to be affected.

Unblinding

1. Emergency unblinding

In case of an emergency, the investigator has the sole responsibility for determining if the unblinding of a subject's treatment assignment is warranted. Subject safety must always be the first consideration in making such a determination. Emergency unblinding for AEs may be performed through an IRT system.

If the investigator decides that unblinding is warranted, the investigator should make every effort to contact the medical monitor before unblinding a subject's treatment assignment unless this could delay emergency treatment of the subject. If a subject's treatment assignment is unblinded, the sponsor must be notified immediately.

2. Inadvertent unblinding

Every effort will be made to blind both the subject and the investigator to the identity of BGB-DXP593 or placebo, but inadvertent unblinding of a subject may occur. If an investigator,

site personnel performing assessments, or subject is unblinded, the unblinding will not be the sufficient cause for that subject to be discontinued from study or excluded from any analyses.

5.4. Incorrect Administration

Any incorrect administration of the study drug should be noted in the subject's medical record and on the appropriate electronic case report form (eCRF).

Adverse events due to an incorrect administration of the study drug will be recorded on the AE eCRF. Any SAEs associated with an incorrect administration must be reported within 24 hours of awareness via the SAE reporting process as described in Section 9.6.2. Supportive care should be administered as appropriate.

5.5. Dose Interruption or Modification

There will be no dose reduction of study drug.

A subject may temporarily interrupt their infusion of study drug or discontinue their infusion of study drug due to infusion-related reactions or other medical events.

The subject should resume the study treatment within 2 hours of the infusion interruption if the AE is resolved or recovered to Grade 1 (whichever is more severe). If the subject is unable to resume the study drug within 2 hours of the infusion interruption, then the subject should be discontinued from the study treatment and the subject will be replaced.

The treatment modification for infusion-related reactions is provided in Section 9.7.1.

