9.6.7. Reporting Infusion-Related Reactions

The symptoms of infusion-related reactions may include but are not limited to fever, chills/rigor, nausea, pruritus, angioedema, hypotension, headache, bronchospasm, urticaria, rash, vomiting, myalgia, dizziness, or hypertension. Severe reactions may include acute respiratory distress syndrome, myocardial infarction, ventricular fibrillation, or cardiogenic shock. Individual signs and symptoms of an infusion reaction should be recorded each as a separate AE in the eCRF and identified as an infusion-related reaction. Refer to the eCRF completion guidelines for details.

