9.7.1. Managing Infusion-Related Reactions

The symptoms of infusion-related reactions include fever, chills/rigor, nausea, pruritus, angioedema, hypotension, headache, bronchospasm, urticaria, rash, vomiting, myalgia, dizziness or hypertension. Severe reactions may include acute respiratory distress syndrome, myocardial infarction, ventricular fibrillation, and cardiogenic shock.

Subjects should be closely monitored for infusion-related reactions. Immediate access to an Intensive Care Unit or equivalent environment and appropriate medical therapy (including epinephrine, corticosteroids, intravenous antihistamines, bronchodilators, and oxygen) must be available to treat infusion-related reactions.

Treatment modifications for symptoms of infusion-related reactions due to the study drug are provided in [Table 5](#).

Table 5: Treatment Modifications for Symptoms of Infusion-Related Reactions Due to Study Drug

NCI-CTCAE grade	Treatment modification for Study Drug
Grade 1 - mild Mild transient reaction; infusion interruption not indicated; intervention not indicated.	Decrease infusion rate by 50%. Any worsening is closely monitored. Medical management as needed.
Grade 2 - moderate Therapy or infusion interruption indicated but responds promptly to symptomatic treatment (eg, antihistamines, nonsteroidal anti-inflammatory drugs, narcotics, intravenous fluids); prophylactic medications indicated for ≤ 24 hours.	Stop infusion. Infusion may be resumed at 50% of previous rate once infusion-related reaction has resolved or decreased to Grade 1 in severity within 2 hours of the infusion interruption. The subject should be discontinued from study drug if the Grade 2 infusion-related reaction has not resolved or decreased over 2 hours of the infusion interruption. Any worsening is closely monitored. Proper medical management should be instituted as described below.
Grade 3 – severe Prolonged (eg, not rapidly responsive to symptomatic medication and/or brief interruption of infusion); recurrence of symptoms following initial improvement; hospitalization indicated for clinical sequelae.	Immediately stop the infusion. Proper medical management should be instituted as described below. The subject should be withdrawn from study drug treatment.

NCI-CTCAE grade	Treatment modification for Study Drug

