
Grade 4 – life-threatening Life-threatening consequences; urgent intervention indicated.
	
Immediately stop the infusion. Proper medical management should be instituted as described below. The subject should be withdrawn from study drug treatment. Hospitalization is recommended.

Abbreviations: NCI-CTCAE, National Cancer Institute-Common Terminology Criteria for Adverse Events.

NCI-CTCAE Grade 1 or 2 infusion reaction: Proper medical management should be instituted, as indicated per the type of reaction. This includes but is not limited to an antihistamine (eg, diphenhydramine or equivalent), antipyretic (eg, paracetamol or equivalent), and, if considered indicated, oral or intravenous glucocorticoids, epinephrine, bronchodilators, and oxygen.

NCI-CTCAE Grade 3 or 4 infusion reaction: Proper medical management should be instituted immediately, as indicated per type and severity of the reaction. This includes but is not limited to oral or intravenous antihistamines, antipyretics, glucocorticoids, epinephrine, bronchodilators, and oxygen.

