9.7.2. Severe Hypersensitivity Reactions

If hypersensitivity reaction occurs, the subject must be treated according to the best available medical practice as described in the complete guideline for emergency treatment of anaphylactic reactions according to the Working Group of the Resuscitation Council (United Kingdom) ([Soar et al 2008](#)). Subjects should be instructed to report any delayed reactions to the investigator immediately.

In the event of a systemic anaphylactic/anaphylactoid reaction, the infusion must be stopped immediately and the subject discontinued from the study. Systemic anaphylactic/anaphylactoid reactions typically manifest within minutes following administration of the drug/antigen and are characterized by respiratory distress; laryngeal edema; and/or intense bronchospasm; and are often followed by vascular collapse or shock without antecedent respiratory difficulty; cutaneous manifestations such as pruritus and urticaria with/without edema; and gastrointestinal manifestations such as nausea, vomiting, crampy abdominal pain, and diarrhea.

The subject will be administered epinephrine injection and dexamethasone infusion if hypersensitivity reaction is observed. The subject should then be placed on monitor immediately and an Intensive Care Unit should be alerted for possible transfer if needed.

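### Section 5.5 makes restarting the infusion the written default after a narrow set of severe events: a first related non-serious Grade 3 event at a dose level, or an unrelated Grade 3-4 event, outside the reaction rules

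*Protocol*

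**What the plan says.** **The general rule.** Section 5.5 allows a subject to interrupt the infusion "or discontinue their infusion of study drug due to infusion-related reactions or other medical events". For an interrupted infusion: "The subject should resume the study treatment within 2 hours of the infusion interruption if the AE is resolved or recovered to Grade 1". It adds an outer time limit: "If the subject is unable to resume the study drug within 2 hours of the infusion interruption, then the subject should be discontinued". It sends infusion-related reactions, and only those, to Section 9.7.1 for graded handling.

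**The graded rules.** In Table 5 of Section 9.7.1, the entry for a Grade 2 infusion-related reaction is permissive and slows the restart: "Infusion may be resumed at 50% of previous rate once infusion-related reaction has resolved or decreased to Grade 1 in severity within 2 hours". At Grade 3: "The subject should be withdrawn from study drug treatment". At Grade 4: "The subject should be withdrawn from study drug treatment. Hospitalization is recommended". For a systemic anaphylactic or anaphylactoid reaction, Section 9.7.2 says "the infusion must be stopped immediately and the subject discontinued from the study".

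**The pause rule.** Section 3.3, repeated in SAP Section 6.5.2, pauses both drug administration and enrollment at the dose level. The triggers are one related TEAE of Grade 4 or higher, one related treatment-emergent SAE, or related Grade 3 TEAEs in at least 2 subjects at that level.

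**Discretion.** Section 7.7.1 lets the subject or the investigator stop study drug at any time. Its possible reasons include the subject's best interest and significant or persistent AEs as covered in Section 9.7.

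**The concern.** Section 5.5 looks only at where the event stands when the restart is considered, not at how severe it was. A Grade 3 event that falls to Grade 1 within 2 hours meets its condition in the same way as a Grade 2 event does. For events outside Table 5 the wording directs a restart and names no reduced rate. For a Grade 2 infusion-related reaction, Table 5 merely permits one, at half rate. On paper, a Grade 3 event of another kind is therefore treated more permissively than a Grade 2 infusion-related reaction.

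What is at stake is the safety of individual subjects. They are healthy, they gain no health benefit from the drug, and its side effects in humans are unknown (Section 1.4). In that setting, stopping after a severe and possibly drug-related event ought to be the written default, and not a departure from it.

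**Working it through.** No statistical figure bears on this point, so the check sets the stopping and restarting rules side by side. Suppose an event occurs during the infusion, the infusion is interrupted, and the event is resolved or at Grade 1 within 2 hours. The rule that applies depends on its type, relatedness, seriousness and worst grade:

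| Event | Rule | Result |
|---|---|---|
| Infusion-related reaction, Grade 3 or 4 | Table 5 | Withdrawal from study drug |
| Anaphylactic or anaphylactoid reaction | 9.7.2 | Infusion stopped, subject discontinued from the study |
| Other event, related, and Grade 4 or higher or serious | 3.3, first criterion | Administration pauses at the dose level |
| Other event, related, non-serious Grade 3, second or later subject at the level | 3.3, second criterion | Administration pauses at the dose level |
| Other event, related, non-serious Grade 3, first subject at the level | 5.5 only | Default is to resume |
| Other event, unrelated, Grade 3 or 4 | 5.5 only | Default is to resume |

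Only the last two rows are uncovered. In the two Section 3.3 rows the pause reaches drug administration, but the section does not say expressly whether an infusion already under way and interrupted is included.

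The parenthesis in 5.5 about whichever state is more severe does not supply the missing limit. It compares resolution with recovery to Grade 1, both of which describe the event after it has subsided.

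**Subjects to whom the rule applies** (Section 3.1, Table 3), active and placebo alike:
- Per level: 6 + 2 = 8.
- Levels A and B: 2 × 8 = 16. With level C: 3 × 8 = 24.
- The ceiling, including replacements, is 30.

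**Places left for replacements under that ceiling:** 30 − 16 = 14 with two levels; 30 − 24 = 6 with three. A repeated cohort under Section 3.3 would draw on the same places.

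The documents give no rate for such events, and none is assumed.

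**The case against.** The strongest reply is that the remaining set is very small and that a sensible investigator would not restart.

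- The infusion-reaction list in Section 9.6.7 is open-ended ("The symptoms of infusion-related reactions may include but are not limited to"), so many drug reactions during an infusion would come under Table 5.
- For terms not in CTCAE, the Grade 3 description in Section 9.3.2 overlaps the seriousness criteria in Section 9.4. Some related Grade 3 events would therefore be SAEs and trigger the pause.
- The event must arise during a 30-60 minute infusion and subside within 2 hours.
- Section 5.5 offers discontinuation as an alternative to interruption, so its restart sentence operates only once interruption has been chosen. Section 7.7.1 adds a general right to stop.
- Table 5 describes Grade 3 reactions as prolonged, recurrent or needing hospitalization. A Grade 3 event that clears quickly matches them in grade but not necessarily in clinical course.

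All of this stands, and it limits the point to a minor one. It does not close the gap. The rights to stop are permissive, and the AE reason in 7.7.1 refers back to Section 9.7, which covers infusion and hypersensitivity reactions. Interruptions for other causes are also contemplated: 5.5 names other medical events, telemetry runs through the infusion (Section 8.2.5), and Section 9.3.5 mentions abnormal assessments that lead to interruption. That last text is a general definition of clinical significance, so it shows only that such cases are possible.

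A reader might infer that, outside Table 5 and anaphylaxis, discretion alone stands between any transient Grade 3 event and a restart. The documents do not support that: Section 3.3 is mandatory and reaches drug administration for related serious events and for a second subject with a related Grade 3 event. A reader might also infer that 5.5 overrides Table 5 for severe infusion-related reactions. It does not, because 5.5 refers those reactions to Section 9.7.1.

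**Conclusion.** The point holds in a narrow form. For a first related non-serious Grade 3 event at a dose level, or an unrelated Grade 3-4 event, that is neither an infusion-related reaction nor anaphylaxis and recovers within 2 hours, the protocol's default is to restart. Only discretion under 5.5 and 7.7.1 works against it.

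Severity is minor. How often such a case would arise cannot be estimated from the documents, and nothing suggests that it would be common. No endpoint, analysis or sample-size statement depends on it.

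The conclusion rests on two readings. First, relatedness in the first criterion of Section 3.3 is taken to qualify Grade 4 or higher TEAEs as well as SAEs. If it qualified SAEs alone, unrelated Grade 4 events would also trigger the pause, and the unrelated part of the gap would shrink to Grade 3. Second, the Section 3.3 pause is taken to cover an interrupted infusion, although the text does not say so. If it did not, the gap would be wider.

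**What to change.** Replace the restart sentence in Section 5.5 with:

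*The infusion may be resumed within 2 hours of interruption only if the AE has resolved or decreased to Grade 1, no Section 3.3 pause is in force, and the AE was either Grade 2 or lower at its worst or judged by the investigator not related to study drug, subject to Sections 9.7.1 and 9.7.2; otherwise the subject is discontinued from study drug.*

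Drop the unclear parenthesis about which state is more severe.

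This bars a restart after a related event that reached Grade 3 or higher, and it settles whether a Section 3.3 pause covers an interrupted infusion. For unrelated severe events the investigator's judgement remains, but restarting becomes permitted and is no longer directed. That judgement rests on a causality call made within 2 hours by a blinded investigator. A sponsor wanting no such reliance could bar a restart after any event of Grade 3 or higher, at the price of stopping some infusions for unrelated causes.

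The cost is one sentence and an occasional extra replacement. Section 5.3 assigns a replacement to the same treatment as the subject replaced, so another healthy person may be exposed. The spare places shown above can absorb an occasional case.
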